9.1 Analysis variables

The analysis variables consist of baseline participant characteristics, safety, and immunogenicity for primary- and secondary-objective analyses.

Another key variable has to do with implementation of the study. Specifically, given the conduct during the COVID-19 pandemic, study visit windows were extended to optimize visit attendance in Part A. Therefore “primary interval”, defined as days between first and second vaccinations, and “boost interval”, defined as days between second vaccination and boost, are key covariates in Part A.

9.2 Baseline comparability

Treatment arms will be compared for baseline participant characteristics using descriptive statistics.

9.3 Safety/tolerability analysis

Since enrollment is concurrent with receiving the first vaccination, all participants will have received at least 1 vaccination and therefore will provide some safety data.

9.3.1 Reactogenicity

The number and percentage of participants experiencing each type of reactogenicity sign or symptom will be tabulated by severity and treatment arm and the percentages displayed graphically by arm. For a given sign or symptom, each participant's reactogenicity will be counted once under the maximum severity for all injection visits. In addition to the individual types of events, the maximum severity of local pain or tenderness, induration or erythema, and of systemic symptoms will be calculated. Kruskal-Wallis test will be used to test for differences in severity between arms.

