4. COHORT DEFINITION

Participants

Recruitment will target enrolling 127 healthy, HIV-1–uninfected volunteers aged 18 through 50 years (inclusive); 115 vaccine recipients and 12 placebo recipients.

Design

Multicenter, randomized, controlled, double-blind trial

Duration per participant

Part A: 8 months of scheduled clinic visits (main study) plus an adverse event of special interest (AESI) health contact at month 14

Part A Optional Second Boost: additional 12 months of scheduled clinic visits (main study) after the third vaccination

Part B: 18 months of scheduled clinic visits (main study)

Part C: 18 months of scheduled clinic visits (main study)

Estimated total study duration

41 months (includes enrollment, planned safety holds, and follow-up).

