9.3.2 AEs and SAEs

AEs will be summarized using Medical Dictionary for Regulatory Activities (MedDRA) System Organ Class and preferred terms. Tables will show by treatment arm the number and percentage of participants experiencing an AE within a System Organ Class or within preferred term category by severity or by relationship to study product. For the calculations in these tables, a participant with multiple AEs within a category will be counted once under the maximum severity or the strongest recorded causal relationship to study product. Formal statistical testing comparing arms is not planned since interpretation of the magnitude of differences must rely heavily upon clinical judgment.

A listing of SAEs reported to the DAIDS Regulatory Support Center (RSC) Safety Office will provide details of the events including severity, relationship to study product, time between onset and last vaccination, and number of vaccinations received.

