10. SAFETY TABLES AND FIGURES

10.1 List of Tables

SMB reports and Safety FSRs include the following tables.

- Enrollment Report
- Demographics and Study Product Administration Frequencies
- Overall Protocol Status
- Maximum Local Reactogenicity Summary
- Maximum Systemic Reactogenicity Summary
- Adverse Events by Body System and Severity – By Decreasing Frequency
- Adverse Events by Preferred Term and Severity – By Decreasing Frequency – Includes Severe, Life-Threatening or Death Events Only
- Adverse Events by Preferred Term and Severity – By Decreasing Frequency – Includes All Severities
- Adverse Events by Preferred Term and Severity – By Decreasing Frequency – Includes Related Events Only
- Adverse Events by Preferred Term and Relationship to Study Product – By Decreasing Frequency – Includes Events of Any Relationship
- Expedited Adverse Experiences (EAEs) Reported to the Regulatory Support Center (RSC) Listing
- Adverse Events of Special Interest (AESI) Listing
- Medically Attended Adverse Events (MAAE) Listing
- Pregnancy Listing
- HIV Infection Results from Lab and Reported by Site Listing
- Study Product Administration Errors Listing

Safety FSRs include the following additional tables.

- Social Impact Summary
- Local Lab Value Summary Statistics
- Listing of Adverse Events by Treatment Arm, Participant, and Onset Date
- End of Study Diagnostic ELISA Testing Results Listing
- Local Laboratory Values Meeting Grade 1 AE Criteria or Above Listing

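### Reactogenicity is summarised only as the worst grade over all injections, so Part A arms mix two- and three-dose participants and are not on equal exposure with Parts B and C unless everyone in Part A was boosted

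*SAP*

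**What the plan says.** **Summary rule.** SAP section 9.3.1 tabulates and graphs each reactogenicity sign or symptom by severity and arm. For this purpose a participant's "reactogenicity will be counted once under the maximum severity for all injection visits". Worst grades are also formed for grouped local reactions and for systemic symptoms.

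**Test.** The same section adds that a "Kruskal-Wallis test will be used to test for differences in severity between arms". It does not say which arms enter the test and does not account for the number of injections received.

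**Outputs.** Section 10.1 lists a "Maximum Local Reactogenicity Summary" and its systemic counterpart. The reactogenicity graphs in section 10.3 are likewise maximum-grade displays. None is by injection number.

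**Exposure.** For unboosted Part A participants, section 4 gives: "Part A: 8 months of scheduled clinic visits (main study) plus an adverse event of special interest (AESI) health contact at month 14". For boosted participants it gives: "Part A Optional Second Boost: additional 12 months of scheduled clinic visits (main study) after the third vaccination". Section 11.3 shows that the Part A boost depended on consent. Parts B and C have 18 months of visits, and their primary neutralization endpoints (3.2.1 and 3.3.1) are measured after both the second and the third vaccination.

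**The concern.** A worst grade over injections cannot fall as injections are added. Two groups with identical tolerability at each dose will show different worst-grade distributions if one has received more doses. Here the number of doses varies in two ways: within Part A arms, through the optional third dose, and between Part A and Parts B and C.

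Safety and tolerability is the first primary objective in every part. The 1 mcg dose of 3M-052-AF is used only in Part A and the 3 mcg dose only in Part C, so those two levels can be set side by side only across parts. Groups 2 and 4 receive the same protein and the same 5 mcg adjuvant dose, so a reader will naturally compare them. Without a display by injection, the reader cannot separate dose level from dose count, or see whether reactions become worse on repeat dosing.

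**Working it through.** The SAP states no figure for this point, so there is nothing to reproduce. The check establishes which comparisons are affected and then illustrates the size.

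**1. Planned doses of the 3M-052-AF vaccine arms** (schema and sections 3.1.2, 3.2.1, 3.3.1 and 11.3)

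| Group | Vaccinees | 3M-052-AF | Planned doses |
|---|---|---|---|
| 1 (Part A) | 5 | 1 mcg | 2, or 3 with consent |
| 2 (Part A) | 10 | 5 mcg | 2, or 3 with consent |
| 4 (Part B) | 20 | 5 mcg | 3 |
| 7 (Part C) | 10 | 3 mcg | 3 |
| 8 (Part C) | 10 | 5 mcg, Trimer 4571 | 3 |

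The three-dose entries follow the Part B and C objectives. The schema heads the day-168 column as an optional boost for all parts. Those passages need to be reconciled.

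**2. Which comparisons are affected**

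- Groups 3 to 6 with each other: equal planned exposure.
- Groups 4, 7 and 8 with each other: equal planned exposure.
- Group 1 with Group 2: the same plan, unequal only if boost uptake differs.
- Group 1 or 2 with Groups 4, 7 or 8: unequal unless boost uptake in Part A was complete.

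**3. Size of the dose-count effect**

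Assume the same per-dose probability p of reaching a given grade in both groups, independence between doses, and no boosting in Part A. The values of p are assumptions, since the SAP gives none. The proportion whose maximum reaches that grade after k doses is 1 − (1 − p)^k. The gap between three and two doses is p(1 − p)².

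| p | Two doses | Three doses | Gap (points) |
|---|---|---|---|
| 5% | 9.8% | 14.3% | 4.5 |
| 10% | 1 − 0.9² = 19.0% | 1 − 0.9³ = 27.1% | 8.1 |
| 20% | 1 − 0.8² = 36.0% | 1 − 0.8³ = 48.8% | 12.8 |
| 30% | 51.0% | 65.7% | 14.7 |
| 50% | 75.0% | 87.5% | 12.5 |

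**4. Effect of boost uptake**

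If a fraction u of a Part A arm is boosted, and uptake is unrelated to risk, the gap becomes (1 − u) × p(1 − p)². With u = 0.5 it is 0.5 × 8.1 = 4.05 points at p = 10% and 0.5 × 12.8 = 6.4 points at p = 20%. With u = 1 it is zero. The SAP does not give uptake. If reactions are positively correlated within a participant, the gaps also shrink; in the limit where a participant reacts identically every time, they vanish.

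**5. Effect on the Kruskal-Wallis test**

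The maximum grade was simulated 4,000 times per setting, with the same per-dose grade distribution in both arms and independent doses. Two assumed distributions were used for none, mild, moderate and severe: 50/30/15/5% and 30/40/25/5%. Rejection at the 0.05 level, with no true per-dose difference, was:

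- 10 participants with two doses versus 20 with three: about 14%.
- 10 with two doses versus 10 with three: about 10%.
- 10 versus 20, both with three doses: 5% to 6%.

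The first two figures apply only if the test is run across parts and no one in Part A was boosted.

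**The case against.** **The affected comparison is not a stated safety objective.** Safety objectives are set part by part, the 3 mcg objective concerns neutralization, and the pooling of Part A with Part B in section 9.4.1 is for immunogenicity. This is correct and limits the consequence. It does not remove the mixing of two- and three-dose participants inside Groups 1 and 2, and the unnamed arms leave a cross-part test open. Section 9.4.1 also confines that pooling to responses after the second vaccination, a safeguard that reactogenicity lacks.

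**Other outputs help.** SMB reports list severe reactogenicity and discontinuations by participant, and product administration frequencies are tabulated. With 5 and 10 vaccinees in Groups 1 and 2, individual review is feasible. This stands in part: listings do not give rates with per-injection denominators.

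**The illustration is at the upper end.** It assumes independent doses and no boosting. This stands, and the figures should be read that way.

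**Stronger readings that the SAP does not support:**

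- A reader might infer that no 3M-052-AF dose groups can be compared. In fact 3 versus 5 mcg (Group 7 versus Group 4) is on equal planned exposure, and so is 1 versus 5 mcg within Part A if uptake is equal.
- A reader might infer that Groups 2 and 4 must differ. With complete uptake the planned dose counts are the same.
- A reader might extend the point to adverse events as crude ever/never counts over unequal follow-up. Section 9.3.2 grades them: a participant with several in a category "will be counted once under the maximum severity or the strongest recorded causal relationship to study product". No formal test of arms is planned there, onset dates are listed in the Safety FSR, and the SAE listing gives the number of vaccinations received. The AE collection window is not in this document, so no size can be put on a follow-up effect. Splitting AEs at the third vaccination would be undefined for unboosted Part A participants.

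**Conclusion.** The point holds for reactogenicity, and only where the number of doses can differ: within Groups 1 and 2, and between those groups and Groups 4, 7 or 8. There the planned summary and its test combine tolerability per dose with dose count. Under equal, independent per-dose risk and no Part A boosting, the artefact is 8.1 points at 10% per dose and 12.8 points at 20%. True gaps are smaller to the extent that reactions are correlated within participants or the boost was taken up.

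The adjuvant comparison in Part B and the comparisons among Groups 4, 7 and 8 are not affected on planned exposure. The maximum is a legitimate overall summary; the weakness is that it is the only one. This is a cheap improvement to a primary safety display, and it gives no ground for changing the AE tables.

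**What to change.** - In sections 9.3.1, 10.1 and 10.3, add reactogenicity tables and graphs by injection number (1, 2, 3), with recipients of that injection as the denominator.
- For any comparison or Kruskal-Wallis test involving Part A, use the maximum over injections 1 and 2.
- Name the arms that enter the Kruskal-Wallis test.
- Show Part A third-dose reactogenicity separately, as data from those who consented to the boost.
- Keep the overall maximum as a summary.

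The cost is SAP wording and re-runs of table and graph programs on data recorded by injection visit. The downside is more pages and small third-dose denominators in Part A, at most 5 and 10 vaccinees in Groups 1 and 2.

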9.3.2 AEs and SAEs

AEs will be summarized using Medical Dictionary for Regulatory Activities (MedDRA) System Organ Class and preferred terms. Tables will show by treatment arm the number and percentage of participants experiencing an AE within a System Organ Class or within preferred term category by severity or by relationship to study product. For the calculations in these tables, a participant with multiple AEs within a category will be counted once under the maximum severity or the strongest recorded causal relationship to study product. Formal statistical testing comparing arms is not planned since interpretation of the magnitude of differences must rely heavily upon clinical judgment.

A listing of SAEs reported to the DAIDS Regulatory Support Center (RSC) Safety Office will provide details of the events including severity, relationship to study product, time between onset and last vaccination, and number of vaccinations received.

9.3.3 Local laboratory values

Box plots of local laboratory values will be generated for baseline values and for values measured during the course of the study by treatment arm and visit. Each box plot will show the first quartile, the median, and the third quartile. Outliers (values outside the box plot) will also be plotted. If appropriate, horizontal lines representing boundaries for abnormal values will be plotted.

For each local laboratory measure, summary statistics will be presented by treatment arm and timepoint, as well as for changes between baseline and post-enrollment. In addition, the number (percentage) of participants with local laboratory values recorded as meeting Grade 1 AE criteria or above as specified in the Division of AIDS Table for Grading the Severity of Adult and Pediatric Adverse Events will be tabulated by treatment arm for each postvaccination timepoint. Reportable clinical laboratory abnormalities without an associated clinical diagnosis will also be included in the tabulation of AEs described above.

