10.3 List of Graphs

SMB reports and Safety FSRs include the following graphs.

- Maximum Local Reactogenicities
- Maximum Systemic Reactogenicities
- Boxplots for hemoglobin, platelets, WBC, neutrophils, lymphocytes, ALT, and creatinine at baseline and each post-vaccination follow-up visit

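### The Grade 1-or-above laboratory count in SAP 9.3.3 ignores baseline grade, no planned output shows worsening in grade by arm, and the output list in 10.1 omits the promised tabulation

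*SAP*

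**What the plan says.** Section 9.3.3 plans three kinds of laboratory output.

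- **Plots.** "Box plots of local laboratory values will be generated for baseline values and for values measured during the course of the study", by arm and visit, with outliers shown. Where judged appropriate, "horizontal lines representing boundaries for abnormal values will be plotted".
- **Continuous summaries.** For each measure, "summary statistics will be presented by treatment arm and timepoint, as well as for changes between baseline and post-enrollment".
- **Graded count.** The number and percentage of participants with "local laboratory values recorded as meeting Grade 1 AE criteria or above" "will be tabulated by treatment arm for each postvaccination timepoint".

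The section adds that abnormalities which are reportable but have no accompanying diagnosis also enter the AE tables. Under 9.3.2 and 10.1 those tables are by arm and severity, and they go to both the SMB and the FSR.

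For the graded values themselves, section 10.1 names one output: "Local Laboratory Values Meeting Grade 1 AE Criteria or Above Listing". It stands, with the laboratory summary statistics, under the line "Safety FSRs include the following additional tables". Section 10.3 gives both reports "Boxplots for hemoglobin, platelets, WBC, neutrophils, lymphocytes, ALT, and creatinine at baseline and each post-vaccination follow-up visit". Section 9.5.1 has the SMB review unblinded safety analyses about every 4 months.

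**The concern.** Laboratory measures of safety are part of primary endpoint 1 in Parts A, B and C. For that purpose the useful question is how many participants in each arm got worse after vaccination. The graded count in 9.3.3 answers a different one: how many are at Grade 1 or above at a given visit, whatever they were before the first injection.

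The arms are small: 5, 10 or 20 vaccine recipients, with 1 or 2 placebo recipients per group. Chance differences in baseline status between arms therefore carry straight into the table, and the placebo recipients are too few to calibrate them. Section 5 recognises that unrelated events can fall unevenly by chance, but its remedy is the assessed relationship to product, and it is stated for adverse events. Nothing in 9.3.3 offers an equivalent for the laboratory count.

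Two further points follow. A programmer working from section 10 would not know to produce the by-arm count. And a graded value that is not reportable as an AE would not reach the SMB by grade while the trial is running.

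**Working it through.** The SAP states no figure on baseline laboratory grades, so there is nothing to reproduce. The check compares the analysis text with the output lists.

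**Step 1: what the count separates.** Take four hypothetical participants, one analyte, and one postvaccination visit.

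| Baseline grade | Postvaccination grade | In the 9.3.3 count? | Worsened? |
|---|---|---|---|
| 0 | 0 | no | no |
| 0 | 1 | yes | yes |
| 1 | 1 | yes | no |
| 1 | 2 | yes | yes |

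The last three rows contribute identically. The third is a pre-existing abnormality counted as a postvaccination one, and it is counted again at each later visit where it persists. The fourth is a real worsening that the single threshold does not distinguish from no change.

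**Step 2: whether another planned output fills the gap.**

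- Change-from-baseline summaries use values, not grades. They describe a distribution by arm and do not count participants who crossed a grade boundary.
- Box plots include baseline and outliers, but each box is a separate distribution by arm and visit. They do not connect a participant's baseline value to a later one, and abnormality lines are conditional.
- AE tables carry severity, but only for reportable abnormalities. The reporting rules are not in the SAP.
- The FSR listing shows individual graded values. It is not a summary by arm.

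None gives a by-arm count of participants whose grade rose.

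**Step 3: analysis text against output lists.**

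| Output | Promised in | Named in section 10 | SMB | FSR |
|---|---|---|---|---|
| Graded count by arm and timepoint | 9.3.3 | no | – | – |
| Grade 1-or-above listing | – | 10.1 | no | yes |
| Laboratory summary statistics | 9.3.3 | 10.1 | no | yes |
| Box plots, seven analytes | 9.3.3 | 10.3 | yes | yes |
| AE tables by severity, with reportable laboratory abnormalities | 9.3.2, 9.3.3 | 10.1 | yes | yes |

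The tabulation is missing from the list, and the only dedicated graded laboratory output is confined to the FSR.

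**Step 4: weight of one participant.** One persistent baseline abnormality adds 1/n to an arm's percentage at each visit:

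- n = 20 (Groups 3 to 6): 1/20 = 5 points
- n = 10 (Groups 2, 7 and 8): 1/10 = 10 points
- n = 5 (Group 1): 1/5 = 20 points

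How many such participants to expect depends on baseline prevalence per analyte, on persistence and on the eligibility limits. The SAP gives none of these, so no expected count or probability of imbalance is offered.

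**The case against.** The best reply is that baseline is not ignored: 9.3.3 plots it and summarises change from it. A per-timepoint graded count beside change summaries is an accepted convention, and the table is descriptive, with no test attached. Section 10.1 does not claim to be exhaustive, so a listing there can coexist with the tabulation in 9.3.3. The PSRT can request ad hoc safety reports for the SMB, and the protocol may set further requirements for SMB content.

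Much of this stands. The mismatch between 9.3.3 and 10.1 is an omission from the output list, not a conflict between analysis rules. The convention is not an error in itself. What the reply does not supply is any planned view of baseline by grade, or of worsening by arm.

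Two stronger readings are tempting and should be resisted.

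- A reader might infer that pre-existing abnormalities are attributed to the vaccine. They are not: the count is by arm, includes placebo and assigns no cause.
- A reader might infer that the SMB sees no graded laboratory data. It does. Reportable abnormalities reach it by severity in the AE tables, and those that are severe or worse, or related, also appear in the section 10.2 listings. The gap concerns graded values that are not reportable as AEs.

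**Conclusion.** The point holds in a limited form. The 9.3.3 count mixes abnormalities present before vaccination with those that arise or worsen afterwards, and no output named in the SAP separates them by grade and arm. The by-arm count is also absent from section 10.1, and SMB reports contain no dedicated Grade 1-or-above laboratory table or listing.

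The effect is on how clearly a component of the primary safety endpoint can be read. No test or decision rule in the SAP depends on this count. Its practical size rests on how many participants enter with a graded value and how long it persists, which the document does not give. The certain part is the leverage: 5 to 20 percentage points per affected participant, depending on arm size. This is a cheap improvement worth making, not a flaw that undermines the safety analysis.

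**What to change.** - **Section 9.3.3:** add, for each analyte and arm, a shift table from the last pre-vaccination grade to the worst postvaccination grade. Alternatively, restrict the count to postvaccination grades higher than the last pre-vaccination grade. State that the table is per analyte.
- **Section 10.1:** list this table by name, keep the existing listing as support, and place the table in the set that goes to both SMB reports and Safety FSRs.

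The data are already in hand, since 9.3.3 uses baseline and follow-up values for its plots and summaries. The cost is a wording change, one more table program and a few more pages per report. Participants, visits and sample size are unaffected.

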9.3.4 Reason for vaccination discontinuation and early study termination

The number and percentage of participants who discontinue vaccination and who terminate the study early will be tabulated by reason and treatment arm.

